2. ABSTRACT

Background

High-fidelity simulation is an increasingly used teaching tool that is proven to be effective for learning. According to the literature, by gradually increasing stress and emotions, more effective learning can be achieved. However, allowing the simulated patient to “die”, as a deliberate stressor, is controversial. There is no previous research on the educational effect of letting a simulated patient die. We aim to evaluate the effects of simulated unexpected death on skill retention, stress levels, and emotions. We hypothesize that the occurrence of unexpected death will impact skill retention, and will be associated with higher stress levels and stronger emotions.

Methods

After Institutional Research Ethics Board approval, 56 residents and fellows of different medical specialties will be randomized to either the intervention (unexpected death) or control (survive) group. Participants from both groups will have to individually manage a simulated cardiac arrest crisis. In the intervention group, the scenario will end by the death of the simulated patient, whilst in the control group the simulated patient will survive. Each participant will be immediately debriefed by a trained instructor. Three months later, skill retention will be assessed in a similar scenario. Crisis management performance of all scenarios will be rated by 2 blinded raters. Biological stress, cognitive appraisal, and emotions will be measured during both scenarios.

Implications

The impact of simulated unexpected death on skill retention of residents and fellows will provide instructors with evidence to optimize scenario design and approach the role of stress and emotions in simulation-based education.

3. BACKGROUND

Trainers are more frequently employing high-fidelity medical simulation to allow learners to acquire complex skills at minimal risk to real patients.¹ The presence of critical observers during such training invokes a stress response and emotional reactions in participants. Invoking emotional responses, both positive and negative, appears to enhance the participant's memory of the event and can ameliorate learning.² Some educational researchers take advantage of such responses to overcome the challenges presented by workload, rising expectations, and resource limitations to create a memorable simulation learning event.

The utility of stress for enhancing learning is controversial and its use may be a net negative.^{2,3} Stress is closely associated with anxiety and is generally considered a negative occurrence. Cognitive appraisal theory considers the perception of whether the resources available to a person facing a stressful incident are adequate; if they are, then the situation is viewed as a challenge whereas inadequate resources cause the situation to be seen as a threat. Situations perceived as a threat invoke anxiety in the subject and activate biological pathways, specifically in the sympathetic nervous system and the hypothalamic-pituitary-adrenal axis.^{4,5} Endocrine activity causes the subject to be more attentive and perceptive and to develop stronger memories of the threatening events.⁶⁻⁹ There appears to be a direct correlation between the cortisol levels in an individual during an event and the degree of retention of the memory of that event, though heightened cortisol may negatively affect the recall of older memories during the event.⁶ Despite the promising evidence in favour of heightening cortisol during learning, educators almost must consider the consequences of inflicting negative emotions and stress onto participants. The positive effects of cortisol on memory decay as cortisol concentrations increase, ultimately causing impairment of learning and performance at very high levels.⁸ On the other hand, situations appraised as a challenge are not accompanied by cortisol release and may result in less retention.¹⁰

Evidence consistently suggests that learning and retention are affected by emotional states, both positive and negative.¹¹ Positive emotions encourage individuals to absorb greater degrees of high-level information, while negative emotions reinforce the learning of specific details. The translation of knowledge to a new situation is facilitated by positive emotions occurring when the knowledge was gained, while negative emotions that occur during learning improve the individual's recall of detail information pertaining to the specific situation in which they were learning. In carefully balancing the effects of emotions and stress on learning, some educators have used intentional stressors as an effective element in educational efforts.^{3,12} Many potential stressors are present in medical simulation, including time pressures, unfamiliarity of the environment, ineffective medical treatments and bad patient outcomes. The use of a deliberately bad patient outcome has become a particularly heated discussion within the medical education field and there is a scarcity of evidence to support this discussion.

Critical care situations can invoke a powerful stress response and negative emotions in their demand for expedient actions and quick decisions in rapidly changing situations. The death of a patient can have a potent effect on a provider's emotions even if he or she is highly experienced in clinical care.^{13,14} Educators commonly make efforts to prepare medical learners for *expected* death by causing the death of the mannequin in a simulation for which death is the expected outcome.¹⁵ An

unexpected death of the mannequin may occur in a simulation session in which the learner does not correctly manage the situation.^{16,17} The use of unexpected death in simulation is unsupported by evidence.^{15,16,18} Educators in favour of its use propose that unexpected death may help to cement the event as memorable² and thereby enhance learning.^{3,12} The other side of the discussion fears that unexpected death in simulation will exacerbate negative emotions and subject learners to undue stress, including the physical manifestations of stress. Such an experience could also cause psychological damage to participants or lead them to withdraw from simulation research.^{16,18,19} To date, the literature discussing the impact of simulated death on learning has been limited to retrospective surveys and opinion pieces.^{15,16,20} The true effect that unexpected death has on stress levels, performance and retention remains to be seen.

This study aims to elucidate the effect of unexpected death in a simulation scenario on the retention of crisis management skills. We hypothesize that unexpected death will be detrimental to the retention of these skills and will result in increased stress and negative emotions among participants.

4. OBJECTIVES OF THE CLINICAL INVESTIGATION (HYPOTHESIS)

4.1 Primary Objective

Our primary objective is to evaluate the impact of an unexpected simulated death experience on non-technical skill retention at 3 months. We hypothesize that the unexpected death of a simulated patient during a simulated cardiac arrest scenario will impair the retention of this skill.

4.2 Secondary Objectives

Our secondary objectives are:

- (i) To assess if unexpected death of a simulated patient is associated with an impaired retention of technical resuscitation skills.
- (ii) To examine if unexpected death of a simulated patient is associated with future higher stress levels and stronger emotions during simulated crisis.
- (iii) To investigate the relationship between stress levels as well as emotions and future performance in crisis.

We furthermore hypothesize, that simulated death will lead to higher stress levels as well as more negative emotions and will thereby impact the ability to retain critical skills.

5. DESIGN OF THE CLINICAL INVESTIGATION

This study will be designed as multi center, investigator blinded, randomized, controlled, prospective trial with qualitative and quantitative methodology.

5.1 Population

5.1.1 Subject population

Residents and fellows of the departments of anesthesiology, critical care, emergency medicine, medicine, obstetrics and gynecology, surgery and family medicine at the University of Ottawa and the University of Toronto, including all subspecialties, will be invited to participate in this trial. Participants will be recruited by means of personalized contact via email, phone invitations and poster-advertisement at the respective departments.

5.1.2 Inclusion criteria

Participants will be enrolled after approval of the respective site coordinator. Participants are required to refrain from physical strains, smoking, drinking caffeinated or low pH beverages and

eating for at least one hour before enrollment. Furthermore participants will be included between 11 AM and 8 PM, when cortisol levels are most stable.

5.1.3 Exclusion criteria

Residents with physical burden limiting their ability to manage simulated crisis and pregnant women will be excluded. Participants with a known endocrine disease or taking corticosteroids will not be enrolled.

5.1.4 Withdrawal of participants

Criteria for withdrawal

Participants may prematurely discontinue from the investigation at any time.

Participants must be withdrawn under the following circumstances:

- at their own request
- if the investigator feels it would not be in the best interest of the subject to continue
- if the subject violates conditions laid out in the consent form / information sheet or disregards instructions by the clinical investigation personal

In all cases, the reason why participants are withdrawn must be recorded in detail in the case report form (CRF). Should the investigation be discontinued prematurely, all investigation materials (complete, partially completed and empty CRFs) will be retained.

6. METHODOLOGY

Institutional ethics approval will be sought from the Ottawa Hospital Research Ethics Board and the University of Toronto Research Ethics Board for Health Sciences. Informed consent and a confidentiality agreement will be obtained from participants. Participants will be enrolled after approval from their resident site coordinator. They are asked to refrain from physical strains, smoking, drinking caffeinated or low pH beverages and eating for at least one hour before participating. The trial will be conducted between 11 AM and 8 PM to warranty stable cortisol levels. All participants will be asked to switch off their mobile phones and pagers in order to prevent distraction during the study.

Initial Test

After a standardized accommodation phase of 15 minutes, all participants will be exposed to a prerecorded, 15 minute long video-review of the actual advanced cardiac life support algorithms. We will collect baseline data including demographic data, stress markers and data on anxiety thereafter as described below.

Immediately before a short scenario briefing the participants will be randomized to either the intervention (unexpected death) or control (survive) group. Participants from both groups will have to individually manage a simulated in-hospital cardiac arrest scenario as team leader (Appendix C). At the initial test, in the intervention group (unexpected death), the scenario will be designed to ultimately lead to the death of the simulation mannequin, regardless of the participant's performance. In the control group (survive), the mannequin will survive. We will attempt to ensure that participants do not anticipate the series of events in the retention resuscitation scenario based on their experience during the initial resuscitation scenario (recall bias). Therefore, the scenarios will be different in terms of order of the presenting arrhythmia. For example the participant who manages a patient with ventricular fibrillation (VF), then pulseless electrical activity (PEA), followed by asystole in the initial scenario will go on to manage a patient with pulseless electrical activity (PEA), then ventricular fibrillation (VF), then return of spontaneous circulation (ROSC) in the retention test. The clinical stems of the scenarios in the initial test versus the retention test will also

differ slightly in order to eliminate the potential for this recall bias described above. In summary, the scenarios are of equal complexity, but differ primarily with respect to the clinical context, initial cardiac arrest rhythm and pre-determined outcome (Appendix C).

Two well-trained confederates will act as registered nurse and as respiratory therapist within the team. These roles were prescribed to ensure standardization for each participant. The confederates will be instructed to help and to perform tasks when directed but not to offer crisis management advice or differential diagnoses. An individualized, video-assisted, instructor-led, structured debriefing lasting 30 minutes will follow the initial scenario. As suggested by Gaba, highly experienced and well prepared instructors will lead the debriefing phase in order to deal with potential upcoming emotions and issues.¹⁹ All scenarios and debriefings will be video recorded for performance analysis.

Retention Test

Previous data have shown that, even with high-fidelity simulation, resuscitation knowledge and skills deteriorate between as early as 2 weeks and 1 year after the learning intervention, with a faster decay in skill.^{21,22} Therefore a retention test is planned 3 months after the initial test. After a short accommodation phase of 15 minutes and assessment of baseline data a standardized scenario briefing will be done. Participants from both groups will be asked to be team-leader in a cardiac arrest scenario to test for skill retention. Again, two confederates, one acting as registered nurse and one acting as respiratory therapist will be team members. While the scenarios will be the same as in the initial test, the case presentation of the scenario and the mannequin “outcome” will be switched for the retention test. The mannequin will survive for the “unexpected death” group and it will die in the “survive” group. That way, each participant will be exposed to simulation death in the study once. To maximize learning opportunities for participants in this study, an individualized debriefing with a specially trained facilitator will follow the retention test as well.

All scenarios and debriefings will be video recorded for further performance analysis.

Following the retention scenario and completion of risk assessment, participants will be interviewed to determine their subjective views of their decision-making and performance within an orally administered survey approximately 30 minutes in length.

Both Phases

The setting and equipment will be the same in the initial and the retention phase, reflecting an appropriately equipped normal ward room at our hospital. SimMan (Laerdal, Stavanger, Norway) will be used as the standardized simulation mannequin in all scenarios. The mannequin will be placed in a patient bed. The mannequin will be operated by an experienced simulation specialist from a separated control room. All scenarios will be peer reviewed and validated by experts in the field of medical simulation and resuscitation. The scenarios will be prescribed for a duration of maximum 15 minutes. The confederates acting as team members during the scenarios will receive extensive precourse training with prescribed responses and interactions. Predefined, peer reviewed cues will be given by the supporting staff in case the participants fail to recognize the cardiac arrest situation. These cues will include the repetition of the case presentation and vital parameters.

Each phase is accompanied by assessment of baseline data, stress parameters and emotions. All scenarios and debriefings will be video recorded to allow performance assessment by two independent experts raters blinded to group allocation.

In order to collect meaningful qualitative data from a maximum of subjects, all subjects will be exposed to unexpected death either during their initial or retention scenario. Subjects of group “unexpected death” will have their simulated patient survive during the retention test while subjects from the group “survive” will have their patient die during the retention scenario. The course of both

subsets of scenarios is the same up until the final two minutes, and the final outcome of the scenarios will not be seen by the expert raters. Therefore, we do not consider this trial as a crossover design.

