6.1.3 Stress Assessment

Acute stress will be assessed by means of salivary cortisol, the State-Trait Anxiety Inventory (STAI) and questionnaire aligned with the cognitive appraisal theory.^{4,5,10,25}

Salivary Cortisol

The activation of the hypothalamic-pituitary-adrenal axis as surrogate for psychological stress will be measured using salivary cortisol levels that show a close to linear relationship to plasma cortisol levels.^{4,5,26} Cortisol levels will be measured in both simulation tests (initial test and retention test). Salivary cortisol peaks at 20 to 40 minutes after the onset of a stressor.⁴ In order to approach cortisol kinetic, 5 cortisol samples will be obtained per participant per scenario: when participants arrive at the simulation center (sample 0), just before each scenario (sample 1), immediately at the end of the each scenario (sample 2), 30 minutes after the start of the scenario (sample 3), and at the end of the debriefing phase (sample 4). The cortisol sampling schedule for the initial and the retention test will be identically, resulting in a total of 10 cortisol samples per participants (see Appendix D). A roll shaped synthetic saliva collector (Salivette for Cortisol testing, Starstedt, Montreal, Quebec, Canada) will be used and will be frozen at -20°C until analysis using an ELISA technique at the Technische Universität Dresden, Germany.

State-Trait Anxiety Inventory (STAI)

To evaluate acute and subjective stress the standardized test battery of the STAI will be used. With STAI state anxiety at the very given moment can be measured using 20 statements to which the participants agree or disagree on a four point Likert-like scale (1 – not at all, 4 very much so). The sub scores are summed up and provide a sensitive basis for acute changes in anxiety related to stressful simulation.^{10,25} STAI will be assessed after the resting phase before each scenario and immediately after the debriefing of the initial and the retention scenario.

Cognitive Appraisal

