6.1.4 Emotion Assessment

Emotions are inevitably linked to the occurrence of expected and unexpected death while treating a patient or patient simulator.¹⁶ As these feelings may foster or impair the learning effect, emotions that occurred throughout the simulation scenarios will be assessed. Participants will be asked to classify their emotions they experienced throughout the study by using the established Positive and Negative Affect Schedule (PANAS) at the end of each scenario. This assessment will be done immediately after debriefing of the respective scenarios.

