7.1.2 Secondary outcome parameters

Secondary outcomes will be (i) technical resuscitation skills (performance and retention) measured by the American Heart Association's Megacode Checklist (ii) stress including salivary cortisol, cognitive appraisal and STAI and (iii) valence of emotions.

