Five-point Likert scale

Repeated measures ANCOVA:

- Dependent variable: Score for each emotion
- Independent variable: Death vs. survival
- Covariates: Junior vs. senior; Acute vs. non-acute
- Time points: Initial and retention

For all Outcomes:

Relationships between all outcomes (determined by ANCOVA or by Pearson’s correlation) will be presented in a matrix table.

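### The emotion model leaves out the pre-randomisation STAI score that the trial already collects, so between-group emotion contrasts are somewhat less precise than the data allow

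*Protocol*

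**What the plan says.** Protocol section 7.1.2 lists emotion among the secondary outcomes ("iii) valence of emotions"), and section 4.2 gives it a directional hypothesis.

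On timing, section 6 (Initial Test) puts baseline collection after the video review: "We will collect baseline data including demographic data, stress markers and data on anxiety thereafter as described below". Allocation comes next: "Immediately before a short scenario briefing the participants will be randomized". Section 6.1.3 adds that "STAI will be assessed after the resting phase before each scenario", with a second administration after debriefing.

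Emotion is handled differently. Section 6.1.4 has participants classify their emotions "by using the established Positive and Negative Affect Schedule (PANAS) at the end of each scenario", and then fixes the moment: "This assessment will be done immediately after debriefing of the respective scenarios". The general statement in section 6 (Both Phases), "Each phase is accompanied by assessment of baseline data, stress parameters and emotions", names emotions separately from baseline data and gives no pre-scenario time for them.

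The SAP analyses each emotion score by repeated measures ANCOVA over the initial and retention tests, with "Covariates: Junior vs. senior; Acute vs. non-acute". Neither a baseline emotion score nor the STAI appears in that model.

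**The concern.** The first PANAS follows the death or survival ending, so it cannot serve as a baseline. How a participant felt on arrival is therefore unadjusted in any comparison between arms, both as residual variance and as chance imbalance in a trial of 56. The other stress measures have a pre-scenario reading: cortisol is analysed as change from baseline, and STAI and cognitive appraisal are taken before and after the scenario. Emotion has none.

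One pre-randomisation measure plausibly related to negative affect, the STAI state score, is already collected at that sitting. Protocol section 8.2 describes the study as limited by its sample size, so precision available without new participants or new data is worth taking. What is at stake is the width of the confidence interval for the emotion contrast, not its validity.

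**Working it through.** **Inputs from the documents.** 1:1 allocation (Protocol 6.2); two-sided 5% level, d = 0.8, r² = 0.12, 46 analysable and 56 recruited (Protocol 7.2); two stratum covariates (SAP, Secondary Outcome 3). No power or sample size is stated for emotion.

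**Assumed inputs.** r, the correlation between baseline STAI and the later emotion score after adjustment for the strata, and d for emotion. Neither is in the documents. I show r from 0.2 to 0.4, and d of 0.65 and 0.8; the 0.8 is borrowed from the primary outcome.

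**The plan's own figure.** A two-sample t-test at d = 0.8 and 80% power needs 25.5, so 26 per arm and 52 in total. Then 52 × (1 − 0.12) = 45.76, so 46; and 46 × 1.2 = 55.2, so 56. The stated numbers reproduce. They belong to the primary outcome, and this point does not change them.

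**Variance ratio with one added covariate, degrees of freedom charged.** (1 − r²)(n − 5)/(n − 6). At n = 56 the last factor is 51/50 = 1.02.
- r = 0.2: 0.96 × 1.02 = 0.979
- r = 0.3: 0.91 × 1.02 = 0.928, equivalent to 56/0.928 ≈ 60 participants without the covariate
- r = 0.4: 0.84 × 1.02 = 0.857, equivalent to 56/0.857 ≈ 65 participants

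**Power for a between-group contrast at one session.** Non-central F with 1 and n − 2 − q degrees of freedom (q = 2 for the strata, 3 with STAI) and non-centrality n(d/2)²/(1 − r²). For n = 56 and d = 0.65, this is 56 × 0.325² = 5.915 without STAI, and 5.915/0.91 = 6.50 at r = 0.3.

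| Covariates | n = 56, d = 0.65 | n = 56, d = 0.8 | n = 46, d = 0.65 |
|---|---|---|---|
| Strata only | 67% | 84% | 58% |
| + STAI, r = 0.2 | 68% | 85% | 59% |
| + STAI, r = 0.3 | 71% | 87% | 62% |
| + STAI, r = 0.4 | 74% | 89% | 65% |

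The 56 suits the initial-test contrast, which precedes loss to follow-up. The 46 suits an analysis of those who complete both tests.

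**Which contrast gains.** The SAP does not say which effect of the repeated measures model is the test. A simulation (6,000 runs, n = 46, equal correlation r among baseline, initial and retention scores, unit variance) gave these standard errors without and with the baseline covariate:

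| Contrast | r = 0.3 | r = 0.5 |
|---|---|---|
| Groups at initial test | 0.299 → 0.290 | 0.298 → 0.261 |
| Groups, average of both tests | 0.243 → 0.229 | 0.257 → 0.213 |
| Group by time | 0.351 → 0.354 | 0.304 → 0.308 |

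The group-by-time contrast already removes stable differences between persons, so the covariate adds nothing there.

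**The case against.** The strongest reply is that the benefit depends on a contrast the SAP has not named. Outcomes are switched at retention (Protocol 6, Retention Test), so each participant meets one death and one survival, and group by time is the contrast that sets one against the other within a person. The gain there is about nil. This stands, and it confines the point to between-group contrasts. The average over sessions also mixes one death and one survival in each arm, which no baseline covariate cures. The initial-test difference is where the gain is most useful.

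Second, r is unsupported and may be low. The SAP's dependent variable is each emotion on a five-point scale, which suggests single items; these tend to be less reliable than subscale totals. STAI is a proxy, probably weaker for positive affect and for a score three months later. A scenario and a 30-minute debriefing come between the two measurements. All this stands, and it is why the range stops at 0.4.

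Third, emotion is one of several secondary outcomes, no power is claimed for it, and Protocol 8.2 calls every aspect of the study hypothesis-generating. That lowers the priority but is no reason to leave a collected covariate unused.

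A reader might infer that the missing baseline biases the emotion comparison. It does not: randomisation protects the contrast, and a question about change within an arm is not the randomised question. A reader might also expect larger gains, on the view that a baseline PANAS would be the same instrument given twice. Section 6.1.4 asks about emotions over the whole study, so a baseline asking how the participant feels now would be a different measurement, and no document supports a high correlation.

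Finally, the baseline list in section 6 is not exhaustive, and Appendix D was not available to check. Section 6.1.4 is nevertheless explicit on when PANAS is given.

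**Conclusion.** The point holds as a modest, cost-free gain in precision. The emotion model omits a valid pre-randomisation covariate that the trial already collects. If r after stratum adjustment is 0.3 to 0.4, the variance of the initial-test contrast at n = 56 falls by about 7% to 14%. Power rises by about 4 to 7 points at d = 0.65 and by about 3 to 6 points at d = 0.8. With 46 analysable participants and d = 0.65 it goes from 58% to between 62% and 65%. At r of 0.2 or less the gain is negligible (about 2% of variance). It is probably smaller for positive affect and for single items, and about nil for group by time.

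The documents do not support calling the comparison biased, treating the planned sample size as affected, or saying that a pre-randomisation PANAS is required.

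**What to change.** In SAP Secondary Outcome 3, add to the covariates the STAI state score taken before the initial scenario and before the allocation envelope is opened. State that the retention-day STAI is not used, because it is post-randomisation. Protocol 6.1.3 and 6.2 both refer to the end of the resting period, so the SAP line should say outright that this STAI precedes the envelope, as the order of events in section 6 implies. The same line can name the contrast to be tested, since the benefit depends on it.

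The cost is one SAP sentence and one degree of freedom, with no new data. It should be prespecified before anyone sees emotion data by arm.

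A pre-randomisation PANAS is an optional further step. It needs a protocol amendment and a few minutes of participant time, and it might cue participants whom section 6.3 keeps blind to the nature of the study. The fix does not depend on it.
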